#### **3.3.3.2. Clinical Laboratory Evaluations**

Laboratory values will be assigned toxicity grades when available using the NCI CTCAE version 5.0 or later. For analytes without a toxicity grading scale, results will be categorized as low, normal, or high based on the laboratory normal ranges.

#### **3.3.3.3. Vital Signs**

Vital signs include systolic and diastolic blood pressure, heart rate, respiratory rate, oxygen saturation, and body temperature.

#### **3.3.3.4. Height and bone age**

Height and bone age will be collected for patients 12 – 18 years (inclusive). Patients without epiphyseal closure at the time of screening will have a bone age left wrist radiograph performed [REDACTED].

#### **3.3.3.5. Ophthalmology Examination and Visual Acuity**

A baseline ophthalmology exam will be performed for all patients at [REDACTED]. If the patient has noted any visual changes, ophthalmology exam will be conducted prior to the start of each new cycle starting with [REDACTED]. If any visual changes are noted at [REDACTED] [REDACTED] visit an ophthalmology exam will be conducted. Acuity of right and left eyes will be measured in logMAR.

#### **3.3.3.6. Assessment of Change in Pubertal Development (Tanner Stage)**

For patients 12 to < 18 years of age, pubertal stage will be measured according to the Tanner Stages [REDACTED] while on active treatment through sexual maturity (Marshall and Tanner 1969, Marshall and Tanner 1970). For female patients, age at menarche will be recorded.

### **3.3.3.7. Electrocardiograms (ECGs)**

ECG parameters include heart rate (bpm), PR (msec), RR (msec), QRS (msec), QT (msec), and QTcF (msec). ECGs will be collected in triplicate at select timepoints (Screening, [REDACTED] and [REDACTED]) after ensuring patient has been resting for at least 5 minutes. For all continuous ECG measurements, triplicate data at each timepoint will be averaged prior to analysis.

Each ECG reading will also be categorized as normal or abnormal based on the interpretation of the assessment by the investigator and, if deemed abnormal, will also be categorized as clinically significant or not clinically significant.

### **3.3.3.8. Echocardiogram/MUGA**

Echocardiogram/MUGA assessments will be performed at select time points ([REDACTED] [REDACTED]) to measure left ventricular ejection fraction (LVEF) percent. Each ECHO/MUGA reading will also be categorized as normal or abnormal based on the interpretation of the assessment by the investigator and, if deemed abnormal, will also be categorized as clinically significant or not clinically significant.

### **3.3.4. Pharmacodynamic Variables**

The pharmacodynamic effects of tovorafenib will be measured by assessing both [REDACTED] [REDACTED] on tumor biopsies obtained at baseline [REDACTED] and [REDACTED]

### **3.3.5. Pharmacokinetic Samples**

Blood for tovorafenib concentration measurements in plasma samples will be collected on all patients in the study. Blood sample collections will occur on [REDACTED] and [REDACTED]

## **3.4. Patients Disposition and Evaluability**

### **3.4.1. Patient Disposition**

Patient disposition will be presented for all enrolled patients by cohort and overall. The number and percentage of patients enrolled, included in each analysis set, and those who complete treatment and who complete the study will be presented. The number and percentage of enrolled patients who discontinue study treatment and discontinue from the study, and the primary reasons for treatment and study discontinuations will also be presented.

All patient disposition data will be presented in listings.

### **3.4.2. Protocol Deviations**

All protocol deviations will be shown in a patient listing. Number of subjects with major protocol deviations will be tabulated by deviation type.

## **3.5. Demographics and Baseline Characteristics**

### **3.5.1. Demographics**

The following demographics and baseline characteristics will be summarized by cohort and overall for the Efficacy Analysis Set and Safety Analysis Set.

- Age (years)
- Age group: 12 years to <18 years, >=18 years
- Race
- Ethnicity
- Sex
- Height and weight
- Body Surface Area (BSA)
- Number of prior therapy lines
- BRAF fusion (Yes, No)
- CRAF/RAF1 fusion (Yes, No)
- CRAF/RAF1 amplification (Yes, No)
- ECOG Performance Status
- Tumor types (tissue agnostic cohort)

Demographics and baseline characteristics will be presented in a patient listing.

### **3.5.2. Medical History and Malignancy History**

Frequencies and percentages will be presented for primary tumor diagnosis and stage at initial diagnosis by cohort and overall for the Safety Analysis Set.

Medical history will be coded by MedDRA 24.0 or higher version.

By-patient listings for medical history and malignancy history will be provided.

### **3.5.3. Concomitant Medications/Therapies**

Concomitant medications are those taken on or after the date of first dose of study treatment or those started before the first dose of study drug and are continuing at the time of the first dose of study drug. All medications taken from 28 days prior to enrollment through 30 days following the last dose of study drug will be recorded in the eCRF. Similarly, surgeries or palliative radiotherapy that are undergone 28 days prior to enrollment through 30 days following the last dose of study drug will be recorded in the eCRF.

Concomitant medications will be coded using the World Health Organization (WHO) Drug Dictionary Enhanced (WHO-DDE, Version B3 September 2021) and classified by Anatomical Therapeutic Class (ATC) Level 3 and PT. Frequencies and percentages of patients using each concomitant medication will be presented for each cohort and overall for the Safety Analysis Set.

The summary will be sorted alphabetically by ATC level 3 term, and within ATC level 3 term, by decreasing PT frequency for all patients.

All concomitant medications and therapies will be presented in patient listings.

#### **3.5.4. Prior Anti-cancer Therapy**

The number and percentage of patients received any prior systemic anti-cancer therapy and received any prior radiotherapy will be summarized, the best response to selected types of prior therapies will be included in the table.

By-patient listings for prior systemic anti-cancer therapy, and prior and concomitant radiotherapy will be provided.

### **3.6. Treatment Compliance and Exposure**

#### **3.6.1. Compliance to Study Treatment**

Treatment compliance will be calculated for each dosed patient as: Treatment Compliance (%) = total actual dose (mg)/ total expected dose(mg)  $\times 100$ .

Treatment compliance will be summarized with descriptive statistics. Number and percentage of patients who had drug interruptions, drug reductions, or drug discontinuations will be also provided.

#### **3.6.2. Exposure to Study Treatment**

Descriptive statistics will be displayed for treatment duration (weeks), total number of cycles treated. Treatment duration (weeks) will be calculated as follows: [(date of last dose of study drug – date of first dose of study drug + 1)/7]. Patients will be counted as treated for a cycle if they received any study drug during that cycle.

All treatment exposure data will be presented in patient listings.

### **3.7. Efficacy Analysis**

Each analysis of clinical efficacy endpoints will be performed with the efficacy analysis set, unless specified otherwise. All efficacy analyses will be presented by cohort, unless specified otherwise.

Efficacy analysis variables are defined in Section 3.3.

#### **3.7.1. Tumor Response**

ORR is defined as the percentage of evaluable patients meeting criteria of radiological CR or PR, confirmed at a subsequent time point ( $\geq 4$  weeks), as assessed by the Investigator.

The ORR and number and percentage of patients meeting the best overall response criteria of CR and PR based on RECIST 1.1 or RANO criteria will be displayed, as well as the number and percentage of patients with the best overall response of CR, PR, SD, PD, not evaluable or with missing response. Exact 95% confidence intervals (CI) will be presented for the ORR, CR, and PR percentages.

For responders, analyses of DOR and time to response will be presented. DOR is defined as the number of days from first tumor response to radiographic disease progression based on RECIST 1.1 or RANO criteria or death by any cause, whichever occurs earlier. Censoring rules similar to those for PFS will be implemented. Summary statistics (25th percentile, median, 75th percentile, and the corresponding 95% CIs) will be presented for DOR using the Kaplan-Meier method.

Descriptive statistics will be presented for time to response, calculated as the number of days from the date of the first dose to date of first response.

All RECIST 1.1 and RANO target/measurable lesions, non-target/non-measurable lesions, new lesions and tumor response will be presented in patient listings.

### **3.7.2. Progression-Free Survival**

PFS is defined as the interval from the date of the first dose to radiographic disease progression based on RECIST 1.1 or RANO criteria or death by any cause, whichever occurs first. Details regarding censoring are included in Appendix 6.3.

Disease progressions reported during the long-term follow up period will be included in the derivation of PFS. The number and percentage of patients who experienced event and censoring will be presented with the corresponding reason as listed in Appendix 6.3. Summary statistics (25th percentile, median, 75th percentile, and the corresponding 95% CIs) will be presented for PFS time using the Kaplan-Meier method.

### **3.7.3. Overall Survival**

OS time is defined as the interval from the date of the first dose until the date of death due to any cause. The number and percentage of patients who died, survived, and were lost to follow-up at the end of the study will be presented. For assessment of OS, data from surviving subjects will be censored on the date when they were last known to be alive. Summary statistics (25th percentile, median, 75th percentile, and the corresponding 95% CIs) will be presented for OS time using the Kaplan-Meier method.

## **3.8. Safety Analysis**

Safety will be evaluated by monitoring all adverse events, serious adverse events, adverse events of special interest, and abnormalities identified through physical examinations, vital signs, and laboratory assessments. Such events will be graded using the National Cancer Institute Common Terminology Criteria for Adverse Events, Version 5.0 (NCI CTCAE v5.0). All verbatim adverse event terms occurring on or after first study treatment will be mapped to Medical Dictionary for Regulatory Activities (MedDRA), and adverse event severity will be graded according to NCI CTCAE v5.0. All safety analyses will be performed with the Safety Analysis Set and presented by cohort and overall.

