6.15. Height and Bone Age

Patients 12 – 18 years (inclusive) should have changes in height compared to standard growth curves to monitor potential effects on bone growth.

Patients 12 – 18 years (inclusive) will have a bone age assessment via bone age radiograph of the left wrist during screening. Patients without epiphyseal closure at the time of screening will have a bone age left wrist radiograph performed every 6 months to monitor for the potential risk of growth retardation.

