##### **3.1.2. Reporting of Numerical Values**

Relevant descriptive statistics (n, mean, standard deviation, median, minimum, and maximum) will be calculated for continuous variables. Confidence intervals (CIs) will be provided where appropriate.

Frequencies and percentages will be presented for categorical and ordinal variables, with the frequencies reported as integers and percentages reported with one decimal place. Unless otherwise specified, the percentages will be calculated based on the total number of patients included for the analysis group. Frequencies and percentages for patients with missing data may be presented.

Means, medians, and confidence intervals will be reported to one decimal place more than the data reported on the case report form (CRF) or by the laboratory/vendor. Standard deviations will be reported to two decimal places more than the data.

A month is operationally defined to be 30.4375 days. Six months is operationally defined to be 182.625 days. One year is defined to be 365.25 days.

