### **3.2.2. Safety Analysis Set**

All patients enrolled in the study who receive at least one dose of tovorafenib will be included in the Safety Analysis Set.

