### **3.8.3. Adverse Events of Special Interest**

Adverse events of special interest (AESI) of tovorafenib will be summarized as below based on TEAEs:

- Rhabdomyolysis, based on the SMQ “Rhabdomyolysis”, narrow scope terms
- Ventricular Arrhythmias, based on SMQ “Ventricular tachyarrhythmias”
- Intra-tumoral hemorrhage, based on SMQ “Haemorrhagic central nervous system vascular conditions” and PT Tumour Haemorrhage
- Secondary primary malignancies, based on SMQ “Non-haematological malignant tumours”
- Ocular toxicity, based on MedDRA SOC “Eye disorders”, excluding HLG Ts “Congenital eye disorders (excl glaucoma)”, “Ocular neuromuscular disorders”, and “Ocular neoplasms”
- Decreased growth velocity, based on PT “Growth disorder”, “Growth failure”, “Growth retardation”, “Body height decreased”, “Body height abnormal”, “Short Stature”.

The AESIs will be summarized by group term, PT and highest CTCAE grade.

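### The growth AESI is reported by default over all treated patients, although only adolescents are monitored for growth; an at-risk n/N row should be added.

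*SAP*

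**What the plan says.** SAP 3.8.3 lists six AESIs. The sixth, introduced as "Decreased growth velocity, based on PT" and followed by six growth and height terms, is not among the five in protocol Appendix G. No age restriction is attached to it. On presentation, the section says only: "The AESIs will be summarized by group term, PT and highest CTCAE grade".

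The denominator comes from three other places:

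- SAP 3.8: "All safety analyses will be performed with the Safety Analysis Set and presented by cohort and overall".
- SAP 3.2.2: "All patients enrolled in the study who receive at least one dose of tovorafenib will be included in the Safety Analysis Set".
- SAP 3.1.2: "Unless otherwise specified, the percentages will be calculated based on the total number of patients included for the analysis group".

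Nothing else is specified for this AESI. SAP 3.5.1 uses age group (12 to <18, and 18 or older) only as a baseline characteristic, and the subgroups in SAP 3.2.4 are for efficacy only. The subsections of SAP 3.8 describe no summary of post-baseline height or bone age.

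Growth monitoring is narrower than the Safety Analysis Set. SAP 3.3.3.4 and protocol 6.15 confine height and bone-age follow-up to ages 12 to 18 inclusive. Protocol 6.15 adds: "Patients without epiphyseal closure at the time of screening will have a bone age left wrist radiograph performed every 6 months". Footnote c of SAP Table 2 limits height after baseline to ages 12 to <18.

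**The concern.** A percentage is informative about a risk when its denominator is the group in which that risk was looked for. Here the denominator holds every dosed adult, while the systematic measurements that would reveal slowed growth are made only in adolescents. Adults lower the percentage without contributing growth monitoring.

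The AESI row is the only post-baseline growth summary that SAP 3.8 describes, so its denominator governs what a reader of the tables can conclude. A row of zeros is the least informative case: it looks the same whether many growing patients were followed or none were.

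**Working it through.** **There is no plan figure to reproduce.** The documents state no expected incidence of this AESI and no number or share of adolescents, and the cohort sizes in SAP Table 1 are redacted.

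**Step 1: which denominator applies.** SAP 3.8 sends all safety analyses to the Safety Analysis Set. SAP 3.2.2 puts every dosed patient in it. SAP 3.1.2 makes the whole analysis group the base of a percentage unless something else is specified, and SAP 3.8.3 specifies nothing else. The base is therefore N, all treated patients, in each cohort and overall.

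**Step 2: effect on the percentage.** Let n be the number of treated patients at risk (in the growth-monitored age range, without epiphyseal closure at screening), x the number of them with the AESI, and f = n/N. Assume no qualifying event outside this group.

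- At-risk percentage = x/n
- Reported percentage = x/N = (x/n) × f
- Dilution = (x/n) / (x/N) = N/n = 1/f

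| Assumed f | Dilution 1/f | A 20% at-risk rate is reported as |
|---|---|---|
| 5% | 20-fold | 1.0% |
| 10% | 10-fold | 2.0% |
| 20% | 5-fold | 4.0% |
| 50% | 2-fold | 10.0% |
| 100% | 1-fold (none) | 20.0% |

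All values of f, and the 20% rate, are assumptions. Because f is computed within each column, two cohorts with the same at-risk rate but a different age mix would show different percentages.

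**Step 3: an illustration with assumed N = 40 and n = 4 (f = 10%).**

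- One event: 1/40 = 2.5% as reported, against 1/4 = 25% in those at risk.
- No events: the exact two-sided 95% upper limit is 1 − 0.025^(1/m) for m patients. For m = 40 this is 8.8%; for m = 4 it is 60.2%.

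The SAP plans no confidence interval for AESIs. The limits only show how much less four patients can exclude than forty.

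**Step 4: the age limits side by side.** SAP 3.3.3.4 and protocol 6.15 include 18-year-olds. Footnote c of SAP Table 2 does not collect their height after baseline, and the age groups in SAP 3.5.1 place them with the adults. The at-risk group therefore cannot be defined until these limits agree.

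**The case against.** The strongest reply is that one common, prespecified safety denominator for every adverse event is a coherent convention, and that the reader loses little. SAP 3.5.1 tabulates age group for the Safety Analysis Set by cohort and overall, and SAP 3.8.1 lists all adverse events by patient. A reader can see how many patients under 18 were dosed and who had a growth event. This stands in part: no case is hidden, and the adolescent count can be approximately recovered. It does not give the number with open epiphyses, which no planned table shows, and the age groups do not match the monitored range.

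Two stronger readings are tempting, and the documents support neither.

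- A reader might infer that the rate is in fact diluted several-fold. That needs f of about one third or less, and f is not given. At f = 50% the factor is 2, and at f = 100% there is none. The eligibility criteria are in the sub-protocol, which was not supplied, so they cannot settle it.
- A reader might infer that adults cannot have this AESI, so that the full-set percentage is meaningless. As defined, the AESI is a list of preferred terms without an age limit. Adverse events are collected from every treated patient, and a term such as Body height decreased could be coded in an adult. Systematic growth measurement is confined to adolescents; adverse event reporting is not.

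**Conclusion.** The point holds as a limited one. The plan's default rule puts the growth AESI over all treated patients, while growth is monitored only in adolescents, and no planned table shows the number at risk. If any treated patient lies outside the at-risk group and no qualifying event occurs there, a non-zero reported percentage is lower than the at-risk percentage by the factor f. The direction follows from the text; the size does not, because f is unknown. The range of 1- to 20-fold reflects the assumed values of f and is not an estimate for this trial.

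The consequence is confined to one descriptive secondary safety summary. Individual events remain visible in the listings, and the primary response-rate analysis is unaffected. This is a cheap improvement to a table, not a flaw that undermines the safety evaluation.

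**What to change.** Keep the standard full-set row in SAP 3.8.3, so that a qualifying term coded in an adult, or in an adolescent with closed epiphyses, is still counted. Add wording such as:

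*For Decreased growth velocity, an additional row gives n/N by cohort and overall, with numerator and denominator both restricted to Safety Analysis Set patients in the growth-monitored age range who had no epiphyseal closure on the screening bone-age radiograph. N is shown even when no events occur. Patients in the age range without a screening radiograph are counted separately.*

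The separate count is needed because the protocol's summary of changes records height and bone age as an added assessment, so some patients may have no screening film. The age limit (12 to 18 inclusive in one place, 12 to <18 in another) must be reconciled across SAP 3.3.3.4, footnote c of SAP Table 2 and protocol 6.15 before the flag is programmed.

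The cost is a short SAP addition, one derived flag from age and the screening film, which the plan already collects, and one table row. If the tables already exist, the row can be added in the clinical study report as a documented deviation from the SAP, as protocol section 7 provides. The downside is that the added percentage may rest on very few patients, so n and N should be read with it.

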### **3.8.1. Adverse Events**

Analyses of AEs will be based on treatment emergent AEs (refer to Section 3.3.3.1 for definition). Please reference Section 3.1.6 for the handling of partial date/time in determining treatment emergence.

For the presentation of AE incidences, the SOCs will be sorted by decreasing frequency in overall group, and within SOC, the PTs will be presented by decreasing frequency in overall group and then alphabetically. If a patient has more than one occurrence of the same PT, then the PT will be counted only once for that patient. Similarly, if a patient has more than one PT within the same SOC, the patient will be counted only once in that SOC.

All AEs (including TEAEs and non-TEAEs), treatment-related TEAEs (TRAEs), TEAEs leading to study treatment discontinuation, TEAEs leading to dose reduction, TEAEs leading to dose interruption, serious adverse events (SAEs), TEAE with outcome of death, and all deaths will be displayed in patient listings. Day of AE onset and day of AE resolution relative to the start of study drug dosing will be presented in all AE listings.

### **3.8.2. Summary of TEAEs**

The numbers and percentages of patients who experienced any TEAE, TRAEs, TEAEs with CTCAE grade 3 or higher, SAEs, treatment-related SAEs, TEAEs leading to treatment discontinuation, TEAEs leading to dose reduction, TEAEs leading to dose interruption, TEAEs leading to death, and all deaths will be presented by SOC and/or PT and highest CTCAE grade. An overall summary of the number and percentage of patients in each category will also be presented.

TEAEs with missing relationship will be presented in a by-patient listing.

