8.5. Relationship to Study Drug

The Investigator is required to assess the causality/relationship between each AE and the study drug as not related or related and record the assessment on the source documents and in the CRF AE page. Medical judgment should be used to determine the likely relationship of the AE to the study drug considering all relevant factors including (but not limited to) relevant history, concomitant medical condition, and concomitant medications.

Determination should be based on assessment of temporal relationships, biologic plausibility, association (or lack of association) with underlying disease, and presence (or absence) of a more likely cause.

- **Related:** A causal relationship between medicinal product and an AE is at least a reasonable possibility. The AE cannot reasonably be explained by the patient's clinical state, concomitant medical condition or concomitant therapies, and a temporal relationship exists between the event onset and administration of the study drug.
- **Not Related:** It is plausible that the AE has an etiology other than the study drug (e.g., preexisting condition, underlying disease, concomitant medical condition, or concomitant medication).

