- The Investigator will also consult the Investigator's Brochure (IB) and/or Product Information for marketed products in his/her assessment.
- For each AE/SAE, the Investigator must document in the medical notes that he/she has reviewed the AE/SAE and has provided an assessment of causality.
- There may be situations in which an SAE has occurred, and the Investigator has minimal information to include in the initial report to the Sponsor's Drug Safety Group. **However, it is very important that the Investigator always make an assessment of causality for every event before the initial transmission of the SAE data to the Sponsor's Drug Safety Group or designees.**
- The Investigator may change his/her opinion of causality in light of follow-up information and send an SAE follow-up report with the updated causality assessment.
- The causality assessment is one of the criteria used when Sponsor determines regulatory reporting.

Follow-up of AEs, AESIs, and SAEs

- The Investigator is obligated to perform or arrange for the conduct of supplemental measurements and/or evaluations as medically indicated or as requested by the Sponsor's Drug Safety Group or designee to elucidate the nature and/or causality of the AE or SAE as fully as possible. This may include additional laboratory tests or investigations, histopathological examinations, or consultation with other health-care professionals.
- If a patient dies during participation in the study or during a recognized follow-up period, the Investigator will provide the Sponsor with a copy of any postmortem findings, including histopathology, as applicable.
- The Investigator will submit any updated SAE data to Sponsor within 24 hours of receipt of the information, and should submit follow-up on non-serious AESIs in a similar manner.

Reporting of SAEs and AESIs (serious and non-serious)

SAE/AESI Reporting to Sponsor via the SAE Report and AESI Targeted Questionnaire Forms

The Investigator is responsible for ensuring that AEs are monitored and reported. See Section 8.1.1 for greater details regarding the AE, AESI, and SAE reporting periods.

- Report SAEs and non-serious AESIs by completing the paper SAE form (see next section) in order to report the event within 24 hours.
- For all AESIs (serious and non-serious), the applicable AESI targeted questionnaire form should be submitted with the SAE form or as soon as possible
- Contacts for SAE reporting can be found in the Study Manual.

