### 2.3.3. Final Analysis

Because of the early study termination, all patients will end study after being followed for at least 6 months after the first dose of study drug. At the end of the study, when the last visit occurs for the last patient enrolled, outstanding data queries have been resolved or adjudicated as unresolvable, and the data have been cleaned and finalized, the final analysis of the data will be performed. Once outstanding data queries have been resolved, the database will be locked, and the final analysis of the study will be performed.

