##### **3.1.4. Handling of Missing/Incomplete Values**

Unless otherwise explicitly specified, missing data will not be imputed; observed values will be used in the analyses.

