### **3.1.6. Handling of Missing/Incomplete Date/Time**

All analyses of AEs will be based on the principle of treatment emergence. Treatment emergent adverse events (TEAEs) are defined as new or worsening adverse events occurring on or after the first administration of study treatment until 30 days after the last dose of study treatment or before the start of subsequent therapy, whichever comes first. For missing or incomplete AE start dates, the following criteria will be used to determine whether an AE is treatment emergent:

Missing AE start day:

- If the partial date contains a different month or year from the date of first study dose, then impute it as the first day of the month.
- If it contains the same month and year as the date of first dose, then impute it as date of first dose.

Missing AE start day and month:

- If the partial date contains a different year from the date of first dose, then impute the missing day and month as Jan 01.
- If it contains the same year as the date of first dose, then impute the missing day and month as day and month of first dose.

Completely missing AE date:

- Missing date will not be imputed and AE is considered treatment emergent.

A medication will be considered concomitant if it is taken on or after the date of first dose of study treatment. In order to determine whether a medication with an incomplete or missing start or end date is concomitant, the following criteria will be used:

- If the start date of a medication is on or after the first dose date and the stop date of the medication is missing, that medication is considered concomitant.
- If the start date of a medication is missing and the stop date of that medication falls on or after the first dose date, that medication will be considered concomitant.
- If the start date of a medication is prior to the first dose date and the stop date of the medication is missing, that medication is considered not concomitant.
- If the start date of a medication is missing and the stop date of the medication is prior to the first dose date, that medication is considered not concomitant.
- If both the start and stop dates of a particular medication are missing, that medication will be considered not concomitant.

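### TEAEs with missing relationship go to a listing and, by default, stay out of the TRAE and treatment-related SAE counts, so those two rates could be understated

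*SAP*

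**What the plan says.** SAP 3.8.2 sets out the adverse event tables, beginning with "The numbers and percentages of patients who experienced any TEAE, TRAEs, TEAEs with CTCAE grade 3 or higher, SAEs, treatment-related SAEs". It then covers discontinuations, dose changes and deaths, and ends with one sentence on incomplete causality: "TEAEs with missing relationship will be presented in a by-patient listing". It does not say whether such events enter the related-event tables. The abbreviation list expands TRAE, but no section defines it for an event with no causality entry.

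The default is in SAP 3.1.4: "Unless otherwise explicitly specified, missing data will not be imputed; observed values will be used in the analyses". No exception is made for relationship. SAP 3.1.2 makes it optional to show how many patients have missing data.

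The protocol expects the field to be filled. Section 8.5 states: "The Investigator is required to assess the causality/relationship between each AE and the study drug as not related or related". For serious events, the causality part of Appendix G adds that "it is very important that the Investigator always make an assessment of causality for every event before the initial transmission of the SAE data". SAP 2.3.3 nevertheless allows the final analysis to proceed once "outstanding data queries have been resolved or adjudicated as unresolvable".

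**The concern.** Protocol 7.3.2 requires TEAEs to be tabulated by relationship to study treatment. The SAP recognises a group of events that are neither related nor not related, and does not say where that tabulation puts them. Under the no-imputation default, a blank has the same effect on a related-event count as a judgement of not related. Yet in Protocol 8.5 that judgement is a positive one, which needs another plausible cause, and nobody has made it for a blank.

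The SAP treats a neighbouring gap in the opposite direction. For an adverse event with no date at all, SAP 3.1.6 says: "Missing date will not be imputed and AE is considered treatment emergent". There the uncertain event is included; here it is left out.

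At stake is the accuracy of the related-event rates in a single-arm study reported by cohort, where denominators are small and one patient is visible in the percentage.

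**Working it through.** **No figure to reproduce.** The plan gives no TRAE rate and no rate of missing causality, and the sample-size table (SAP 2.2.2, Table 1) is blacked out. The check is therefore of direction, then of size under stated assumptions.

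**Step 1: which summaries can move.** Of the categories in SAP 3.8.2, only TRAEs and treatment-related SAEs use relationship. Any TEAE, grade 3 or higher, all SAEs, discontinuation, dose reduction, interruption and death do not. The AESI summaries in SAP 3.8.3 are built on TEAEs, without regard to relationship.

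**Step 2: direction.** With no imputation, a blank is not flagged as related, so the event is not in the numerator. The denominator is the number of patients in the analysis group (SAP 3.1.2) and does not change. SAP 3.8.1 counts a patient once per preferred term and once per system organ class. A row therefore falls only if the event was truly related and the patient has no other related event counted in that row. Otherwise it is unchanged. It cannot rise.

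**Step 3: one affected patient.** Shift = 100/N percentage points. With N assumed:
- N = 10: 100/10 = 10 points
- N = 20: 100/20 = 5 points
- N = 40: 100/40 = 2.5 points

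In a sparse row the relative change is large: 2/20 = 10% would print as 1/20 = 5%.

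**Step 4: expected shortfall.** All inputs are assumed. Let p be the true share of patients with a related event in the row, k the number of related events in that row per such patient, and m the probability that an entry is missing, independently of everything else. The printed rate is p × (1 − m^k).

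| p | k | m = 1% | m = 5% | m = 10% |
|---|---|---|---|---|
| 30% | 1 | 29.7% | 28.5% | 27.0% |
| 10% | 1 | 9.9% | 9.5% | 9.0% |
| 30% | 5 | 30.0% | 30.0% | 30.0% |

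For example, 0.30 × (1 − 0.05) = 28.5%. With a single event per patient the relative loss equals m. For a summary of any TRAE in patients with five related events, nothing is visible even at m = 10%. At m = 0 the loss is zero in every row.

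**Step 5: the opposite convention.** If blanks count as related, the rate for any TRAE is p + (1 − p) × (1 − (1 − m)^j), where j is the number of unrelated TEAEs in each patient with no related event. At p = 30% and m = 5%:
- j = 1: 0.30 + 0.70 × 0.05 = 33.5%
- j = 5: 0.30 + 0.70 × (1 − 0.95^5) = 45.8%

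This convention is too high by 3.5 to 15.8 points in the example, against 1.5 points too low (30 − 28.5) for the single-event row in Step 4. Neither count is right alone. Together they bracket the count that complete causality data would have given.

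**The case against.** The strongest reply is that the SAP states a listing and does not say that these events are listed only. Listings accompany tables in this plan: SAP 3.8.1 lists TRAEs, SAEs and deaths that 3.8.2 also tabulates. This is fair. Exclusion from the related counts is an inference from 3.8.2 read with 3.1.4. It is still the reading a programmer would follow, since nothing in the SAP permits a blank to be flagged as related.

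A second reply is that few blanks will survive. Causality is mandatory for each event and is to be given before an SAE report is first sent; the Sponsor's safety physician makes a second assessment of SAEs (Protocol 8.2.2); and eCRFs are not complete until missing data are accounted for (Protocol 9.2). This stands and limits the size, most of all for treatment-related SAEs. It does not remove the gap, because 3.8.2 itself provides for blanks at reporting.

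A third is that the SAP has no general inclusive principle to breach: SAP 3.1.6 classes a medication with both dates missing as not concomitant. This also stands. The contrast with missing event dates is an inconsistency between neighbouring rules, not the breach of a stated policy.

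A fourth is that counting blanks as related sits awkwardly with Protocol Appendix G, where a reasonable possibility needs supporting facts, and that it can overshoot by more than the default undershoots. Step 5 confirms the overshoot. The answer is to present it as a tabulation convention and print both counts.

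A reader might also infer that unresolved queries are likelier because the study closed early. The documents do not say so. SAP 2.2.1 describes at least 6 months of follow-up and data cleaning before the analysis.

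**Conclusion.** The point holds as a minor one. SAP 3.8.2 with 3.1.4 leaves TEAEs with missing relationship out of the TRAE and treatment-related SAE counts, and any resulting error in those two categories is downward. It is zero if no entry is blank at lock, near zero for any TRAE when patients have several related events, and 1/N per affected patient in sparse rows. The sizes shown rest on assumed values of N, p, k, j and m, and on entries being missing independently.

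A reader might go further and conclude that TEAE and SAE rates in general are biased low, or that blanks are treated as not related in every table. The documents do not support either. Most tables ignore relationship, no value is assigned to a blank, and understatement requires a truly related event, still blank at lock, in a patient with no other related event counted in that row. The primary endpoint is untouched, as is the Phase 2 safety endpoint of event incidence and severity (Protocol Table 6).

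**What to change.** Replace the last sentence of SAP 3.8.2 with: *TEAEs with missing relationship are counted as treatment-related in the TRAE and treatment-related SAE tables; the number of patients and events affected is footnoted, with the count excluding them, and the events are also listed.*

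The rule should be fixed before the tables are run, so that it is not chosen with its effect in view. If the SAP can no longer be amended, Protocol section 7 already provides for reporting the deviation in the clinical study report.

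The cost is one SAP sentence, one line of derivation code and a footnote. The downside is that the convention errs high, so related-event rates may rise; the footnoted count without the missing entries shows by how much. If nothing is missing, the tables do not change.
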